1.3 Clinical Data to Date

FDA approval was based on two double blind, Phase III trials on soft tissue and orthopedic surgical models. Subsequent to that, the medication was used in another Phase III trial with patients having bunionsectomies ¹¹. It found that EXPAREL use in 97 patients was associated with better postoperative pain, and no adverse side effects were found. Subsequently, another randomized, double blind, prospective Phase III trial was done, in patients undergoing hemorrhoidectomy ¹². The EXPAREL group (n=94) had less pain, and used less opioid medication. No adverse events were observed.

The safety profile of EXPAREL has been evaluated and in a meta-analysis, and its side effect profile has been found to be similar to bupivacaine. The most common side effects in the 800 patients in the EXPAREL group were nausea (3.3%) and constipation (2.0%). Cardiac complications were tachycardia (4%), and bradycardia (2%), which did not require treatment, and were similar to bupivacaine group. One death was reported in the 800 patients that received EXPAREL, and one in the bupivacaine group; both drugs were deemed as not the causative agents ¹³.

EXPAREL has been used in TAP infiltrations and has been used in two small studies totaling 37 patients. No side effects were reported, and the patients had low pain scores, with minimal narcotic use ^{14,15}.

At our institution, EXPAREL has been used for over one year with hundreds of patients both in the Rochester and Jacksonville campuses without any side effects attributed to EXPAREL injection.

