3.4 Primary Safety Endpoints

Patients will be monitored both intraoperatively and postoperatively for any adverse events (as defined below and in section 8). Patients will be connected to a cardiac monitor intraoperatively, and until the morning of postoperative day 1 (POD1). Patient will also be connected to a continuous pulse oximeter until the morning of postoperative day 1 (POD 1). These are standard practice for the recovery units. The surgical team will assess the patient routinely twice daily, more often if necessary. Vital signs (heart rate, oxygen saturation, and blood pressure) will be captured at least four times per day, more frequently if the clinical situation dictates. In addition, patients will all have a complete blood count, and creatinine checked on POD1 routinely. None of the patients enrolled in the trial will receive any amide-type anesthetics within 72 hours after EXPAREL use.

4 Subject Selection Enrollment and Withdrawal

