7.3 Analysis plans

Patient Population(s) for Analysis

The patient for the primary analysis will be all randomized patients who did not withdraw prior to the initiation of anesthesia. The numbers of patients that withdraw prior to undergoing surgery will be monitored for imbalances between the arms.

Primary analysis plan

The primary analysis will be a modified intent-to-treat analysis. This means it will be an analysis of all randomized patients who did not withdraw prior to surgery according to the arm to which they were randomized.

The mean pain scores over 48 hours will be summarized as the area under the curve (AUC) of the observed pain score (y-axis) plotted by the time it was measured (x-axis). The difference in mean AUCs of the two groups will be evaluated using a two-sample t-test. In addition, the cumulative narcotic use over the 48 hour period will be determined for each patient (standardized OME). The difference in mean standardized OME will be compared with a two-sample test. If the data are skewed, a two-sample t-test will be performed on the logged values of OME or a Wilcoxon rank sum test will be used on the untransformed data. A two-sided p-value will be declared statistically significant for each primary endpoint. This will mean that the overall two-sided level of significance for the trial will be 0.10.

In addition to looking at the summary of the pain scores and OME scores, we will also plot these values over time and determine whether there are differences at individual time points.

Secondary analysis plan

The mean length of stay will be compared between the two groups with a two-sample test. If there are no outliers, a two-sample t-test will be used. If there are outliers, a Wilcoxon rank sum test will be used. A chi-square test (or Fisher's exact test) will be used to compare the rates of POI, need for a PCI and post-operative hypotension.

Comparisons will be made between the randomized groups of the baseline variables (patient, disease, and surgical) to determine if there were any randomization imbalances. If imbalances are found, a secondary analysis will be done using linear regression and adding the variables that were not balanced between the groups.

Descriptive Statistics

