8.1 Definitions

Unanticipated Problems Involving Risk to Subjects or Others (UPIRTSO)

Any unanticipated problem or adverse event that meets the following three criteria:

- Serious: Serious problems or events that results in significant harm, (which may be physical, psychological, financial, social, economic, or legal) or increased risk for the subject or others (including individuals who are not research subjects). These include: (1) death; (2) life threatening adverse experience; (3) hospitalization, readmission, or prolonged hospital stay; (4) disability/incapacity - persistent or significant; (5) birth defect/anomaly; (6) breach of confidentiality and (7) other problems, events, or new information (i.e. publications, DSMB reports, interim findings, product labeling change) that in the opinion of the local investigator may adversely affect the rights, safety, or welfare of the subjects or others, or substantially compromise the research data, **AND**
- Unanticipated: (i.e. unexpected) problems or events are those that are not already described as potential risks in the protocol, consent document, not listed in the Investigator's Brochure, or not part of an underlying disease. A problem or event is "unanticipated" when it was unforeseeable at the time of its occurrence. A problem or event is "unanticipated" when it occurs at an increased frequency or at an increased severity than expected, **AND**
- Related: A problem or event is "related" if it is possibly related to the research procedures.

Adverse Event

An untoward or undesirable experience associated with the use of the medications used in this trial, as bellow:

- Any arrhythmia/ tachycardia/bradycardia necessitating intervention (medicine or cardioversion)
- Vertigo, tinnitus, seizure
- Any myocardial infarction
- Any site infection / hemorrhage / persistent injection site pain, neuropathy or nerve injury
- Postoperative headaches

Serious Adverse Event

Adverse events are classified as serious or non-serious. Serious problems/events can be well defined and include;

- Death
- Life threatening adverse experience
- Hospitalization
- Inpatient, new, or prolonged; disability/incapacity
- Persistent or significant birth defect/anomaly

and/or as per protocol there may be problems/events that in the opinion of the sponsor-investigator may have adversely affected the rights, safety, or welfare of the subjects or others, or substantially compromised the research data.

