8.2 Recording of Adverse Events

At each contact with the subject, the study team must seek information on adverse events by specific questioning and, as appropriate, by examination. Information on all adverse events should be recorded immediately in the source document, and also in the appropriate adverse event worksheet. All clearly related signs, symptoms, and abnormal diagnostic, laboratory or procedure results should be recorded in the source document.

All adverse events occurring during the study period must be recorded. The clinical course of each event should be followed until resolution, stabilization, or until it has been ultimately determined that the study treatment or participation is not the probable cause. Serious adverse events that are still ongoing at the end of the study period must be followed up, to determine the final outcome. Any serious adverse event that occurs after the study period and is considered to be at least possibly related to the study treatment or study participation should be recorded and reported immediately.

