8.5 Adverse Event Stopping Rule

Adverse events will be continuously monitored by the study team for patient safety. Each month, a report of the adverse events and SAEs will be generated. This report will

include the enumeration and tallies of the adverse events (and SAEs) by arm. A chi-square test (or Fisher's exact test, whichever is appropriate) will be used to compare the AE and SAE rates between the arms. If there is a statistically significant difference in SAE rates between the two arms, accrual to the trial will be temporarily suspended while the study team does a thorough evaluation of the SAEs observed. Upon a thorough review of the observed SAEs, the study team and DSMB will make a determination whether to reopen the trial with no amendments, to amend the trial and reopen, or to permanently close the trial.

The monthly SAE rate report will be sent to the DSMB Chair. This will determine whether or not a non-scheduled DSMB meeting needs to be convened prior to the 6 month DSMB review.

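### The adverse event list in section 8.1 omits nausea, constipation, hypotension and desaturation, and the protocol does not say whether it is exhaustive, so the by-arm AE comparison in 8.5 is incomplete for non-serious events

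*Combined protocol and SAP*

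**What the plan says.** Section 8.1 (Adverse Event) defines the term as "An untoward or undesirable experience associated with the use of the medications used in this trial, as bellow". Five bullets follow: rhythm disturbance, a group of neurological symptoms, myocardial infarction, injection-site and nerve events, and headache. No bullet is open-ended. The rhythm bullet carries a threshold: "Any arrhythmia/ tachycardia/bradycardia necessitating intervention (medicine or cardioversion").

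Other sections lean on this definition. Section 3.4 monitors adverse events "as defined below and in section 8". In 8.1, under General Physical Examination Findings, new end-of-study findings are recorded as adverse events only if they satisfy the definition. Section 8.2 adds "All adverse events occurring during the study period must be recorded", which uses the same term. Section 8.5 has a monthly report in which a chi-square or Fisher's exact test "will be used to compare the AE and SAE rates between the arms".

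Section 1.3 gives the expected EXPAREL profile: "The most common side effects in the 800 patients in the EXPAREL group were nausea (3.3%) and constipation (2.0"%), together with "tachycardia (4%), and bradycardia (2%), which did not require treatment". Section 7.3 includes among its secondary by-arm tests "need for a PCI and post-operative hypotension". Section 3.4 has blood pressure, heart rate and oxygen saturation captured at least four times a day.

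**The concern.** The definition of an adverse event decides what enters the safety count. If site staff apply the five bullets as written, the two EXPAREL side effects that the protocol itself names as commonest never reach the monthly tally. Neither does a non-serious fall in blood pressure or oxygen saturation, although both are measured in every patient and one arm receives an intrathecal opioid.

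If staff instead follow the broader passages in 8.1, they will record events outside the bullets. The protocol does not say which reading governs. The trial is unblinded (5.8) and each campus records its data separately (9.2, Data Processing), so the two readings could coexist, even though 7.5 promises the same variable definitions at both sites.

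At stake is what the AE test in 8.5 can show. A comparison of AE rates that leaves out the commonest expected non-serious events cannot describe how the two techniques differ in tolerability.

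**Working it through.** The plan states no figure for adverse event counts, so there is none to reproduce. The arm size comes from the Study Summary: 226 patients at 1:1 gives 226 / 2 = 113 per arm. Section 7.2 uses 100 per arm for power, and that figure reproduces (t-test power 80.4% at an effect size of 0.40 and 94.0% at 0.50, against 80% and 94% stated).

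**Step 1: the list against the events the protocol itself mentions.** Expected count = rate in 1.3 × 113.

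| Event | Rate in 1.3 | On the 8.1 list? | By-arm test elsewhere? | Expected, EXPAREL arm |
|---|---|---|---|---|
| Nausea | 3.3% | No | No | 0.033 × 113 = 3.7 |
| Constipation | 2.0% | No | Not as such (7.3 tests ileus) | 0.020 × 113 = 2.3 |
| Tachycardia | 4% | Only if treated | No | 0.04 × 113 = 4.5 |
| Bradycardia | 2% | Only if treated | No | 0.02 × 113 = 2.3 |
| Hypotension | none given | No | Yes, in 7.3 | not computable |
| Desaturation or respiratory depression | none given | No | No | not computable |

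**Step 2: the size for effects wholly off the list.** (0.033 + 0.020) × 113 = 6.0 events, or 5.3 with 100 patients. Counted as patients, this runs from 3.7 if the two always coincide to 6.0 if they never do. The untreated rhythm events would add (0.04 + 0.02) × 113 = 6.8. They are kept apart because the list covers rhythm events and excludes these only by its threshold.

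**Step 3: what this means between arms.** The documents give no event rates for the intrathecal arm, so a between-arm effect cannot be calculated. As an illustration only, take nausea at 3.3% with EXPAREL and an assumed intrathecal rate p, with 100 per arm and one test at two-sided 0.05 (8.5 states no level). With p̄ the mean of the two rates,

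power = Φ{ [ |p − 0.033| √100 − 1.96 √(2p̄(1 − p̄)) ] / √(0.033 × 0.967 + p(1 − p)) }

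This gives 9% at p = 5%, 48% at 10%, 82% at 15% and 96% at 20%. A large difference in nausea would be detectable if recorded and invisible if not. Nothing in the documents shows that such a difference exists.

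**Step 4: is the list exhaustive?** For the narrow reading: the lead-in with no open item, the cross-reference in 3.4, and the end-of-study rule in 8.1. Against it, also in 8.1: a worsening preexisting condition is to be recorded as an adverse event whatever it is, and the examples of serious events include bronchospasm and drug overdose, neither of which is listed. Section 8.2 does not settle the matter, because its instruction uses the defined term.

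**The case against.** The best defence is that the list was never meant to be closed. Section 8.1 itself goes beyond it twice, 8.2 asks for all adverse events and for related signs, symptoms and abnormal results in the source document, and 7.5 treats adverse event data as complication data. Parts of the gap are also covered elsewhere. Hypotension and ileus are compared by arm in 7.3, and a respiratory event that is life-threatening or prolongs the stay meets the serious criteria. Restricting rhythm events to treated ones is a legitimate choice for a marketed product.

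Much of this stands. The text is inconsistent rather than plainly closed, the rhythm threshold is defensible, and hypotension is not ignored. What remains is that nausea, constipation and non-serious desaturation are in no by-arm analysis under the literal definition, that hypotension falls outside the monthly tally, and that the protocol leaves staff to guess which reading applies. Entry in source documents does not by itself bring an event into the 8.5 test.

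A reader might go further and infer that the list favours one arm. The documents do not support that. The definition covers the medications of both arms, and headache, infection, haemorrhage and nerve injury can follow either injection. With no intrathecal rates, neither direction nor size can be derived.

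**Conclusion.** The point holds for non-serious events. Under the literal definition, the AE comparison in 8.5 would miss about 6 nausea and constipation events per 113 EXPAREL patients, all non-serious hypotension and desaturation, and the untreated rate changes that 1.3 describes. The figure of 6 assumes that the pooled EXPAREL rates in 1.3 apply to bowel resection patients, which the documents do not show. It concerns one arm only.

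Three further inferences should be resisted:

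- That every side effect with a rate in 1.3 is missing. Tachycardia and bradycardia are listed when treated, so the sum 0.113 × 113 = 12.8 mixes absent effects with effects under a threshold.
- That the stopping rule fails. Accrual is suspended on a difference in SAE rates, which does not directly depend on non-serious events.
- That a final safety comparison is spoiled. Section 7.3 specifies no final by-arm AE analysis; the only AE test is the monthly one in 8.5.

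**What to change.** In 8.1, state that the list is a minimum, non-exhaustive set recorded identically in both arms. Add nausea/vomiting, constipation, hypotension, and oxygen desaturation/respiratory depression. Use that set for the AE tallies and test in 8.5. Then reconcile 8.1 with 1.3 (expected effects), 3.4 (monitoring), 7.3 (hypotension) and 8.2 (recording), so that one definition governs throughout. Whether to keep the treatment threshold for rhythm events is for the sponsor to decide; if it stays, say that untreated events are left out on purpose.

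The cost is protocol wording and a few extra fields on the existing adverse event form. Blood pressure, heart rate and saturation are already captured. The documents do not show that nausea and constipation are routinely recorded, so those two may need active questioning in both arms, which 8.2 already asks for at each contact.

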8.2 Recording of Adverse Events

At each contact with the subject, the study team must seek information on adverse events by specific questioning and, as appropriate, by examination. Information on all adverse events should be recorded immediately in the source document, and also in the appropriate adverse event worksheet. All clearly related signs, symptoms, and abnormal diagnostic, laboratory or procedure results should be recorded in the source document.

All adverse events occurring during the study period must be recorded. The clinical course of each event should be followed until resolution, stabilization, or until it has been ultimately determined that the study treatment or participation is not the probable cause. Serious adverse events that are still ongoing at the end of the study period must be followed up, to determine the final outcome. Any serious adverse event that occurs after the study period and is considered to be at least possibly related to the study treatment or study participation should be recorded and reported immediately.

8.3 Reporting of Serious Adverse Events and Unanticipated Problems

When an adverse event has been identified (as previously identified), the study team will take appropriate action necessary to protect the study participant and then complete the Study Adverse Event Worksheet and log. The sponsor-investigator will evaluate the event and determine the necessary follow-up and reporting required.

8.3.1 Sponsor-Investigator reporting: notifying the Mayo IRB

The sponsor-investigator will report to the Mayo IRB any UPIRTSOs and Non-UPIRTSOs according to the Mayo IRB Policy and Procedures.

8.4 Unmasking/Unblinding Procedures

This study is not blinded.

8.5 Adverse Event Stopping Rule

Adverse events will be continuously monitored by the study team for patient safety. Each month, a report of the adverse events and SAEs will be generated. This report will

include the enumeration and tallies of the adverse events (and SAEs) by arm. A chi-square test (or Fisher's exact test, whichever is appropriate) will be used to compare the AE and SAE rates between the arms. If there is a statistically significant difference in SAE rates between the two arms, accrual to the trial will be temporarily suspended while the study team does a thorough evaluation of the SAEs observed. Upon a thorough review of the observed SAEs, the study team and DSMB will make a determination whether to reopen the trial with no amendments, to amend the trial and reopen, or to permanently close the trial.

The monthly SAE rate report will be sent to the DSMB Chair. This will determine whether or not a non-scheduled DSMB meeting needs to be convened prior to the 6 month DSMB review.

8.6 Medical Monitoring

It is the responsibility of the Principal Investigator to oversee the safety of the study at his/her site. This safety monitoring will include careful assessment and appropriate reporting of adverse events as noted above, as well as the construction and implementation of a site data and safety-monitoring plan (see section 10 “Study Monitoring, Auditing, and Inspecting”). Medical monitoring will include a regular assessment of the number and type of serious adverse events.

8.6.1 Internal Data and Safety Monitoring Board

The sponsor-investigator and participating surgeons, as well as the study coordinator will meet once monthly to review any adverse events.

9 Data Handling and Record Keeping

9.1 Confidentiality

Information about study subjects will be kept confidential and managed according to the requirements of the Health Insurance Portability and Accountability Act of 1996 (HIPAA). Those regulations require a signed subject authorization informing the subject of the following:

- What protected health information (PHI) will be collected from subjects in this study
- Who will have access to that information and why
- Who will use or disclose that information
- The rights of a research subject to revoke their authorization for use of their PHI.

In the event that a subject revokes authorization to collect or use PHI, the investigator, by regulation, retains the ability to use all information collected prior to the revocation of subject authorization. For subjects that have revoked authorization to collect or use PHI, attempts should be made to obtain permission to collect at least vital status (long term survival status that the subject is alive) at the end of their scheduled study period.

9.2 Source Documents

Source data is all information, original records of clinical findings, observations, or other activities in a clinical trial necessary for the reconstruction and evaluation of the trial. Source data are contained in source documents. Examples of these original documents, and data records

include: hospital records, clinical and office charts, laboratory notes, memoranda, subjects' diaries or evaluation checklists, pharmacy dispensing records, recorded data from automated instruments, copies or transcriptions certified after verification as being accurate and complete, microfiches, photographic negatives, microfilm or magnetic media, x-rays, subject files, and records kept at the pharmacy, at the laboratories, and at medico-technical departments involved in the clinical trial.

Data Management

Data will be captured in an electronic fashion via institutional database that is already developed

Data Processing

Each campus will record the same data separately; all data will be combined quarterly and interim analysis will be performed.

Data Security and Confidentiality

Access to the data will be provided to only necessary persons, those that collect the data, or need to analyze the data. Data will be stored in a password-protected folder behind the Mayo firewall. All data collection and analysis will be done behind the firewall.

Data Quality Assurance

All data will be entered by appropriately trained personnel, and 1 in 50 records will be "biopsied" for correct data collection.

Data Clarification Process

Incomplete, or erroneous data will be corrected by analyzing the original patient electronic record.

